1.0 Objectives / Specific Aims

Effective control of chronic pain is a top priority in the United States, as approximately 10% of adults have severe chronic pain – most of which is chronic lower back pain (CLBP). However, despite the advances in neuroscience over the past 20 years, we still largely treat chronic pain with opiate narcotics, much as was done in the Civil War. In addition to their high abuse liability and dependence potential (1), only 30–40% of chronic pain patients declare they receive satisfactory (>50%) relief from their pain through pharmacological treatment (Attal et al., 2006). In these patients a common clinical practice is to escalate the dose of opiates as tolerance develops – which unfortunately has contributed to escalation in opiate overdose deaths (2), a resurgence of intravenous heroin use, and \$55 billion in societal costs (3). **Consequently there is a critical need for new, treatments that can treat pain and reduce reliance on opiates in individuals with chronic pain.**

The goal of this R21 proposal is to evaluate 2 novel non-invasive brain stimulation strategies to mitigate pain and the brain's response to pain in CLBP patients that are currently taking chronic opiates, or that are seeking an alternative treatment for pain. Transcranial Magnetic Stimulation (TMS), can induce long term potentiation (LTP-like) and long term depression (LTD-like) effects on brain activity in a frequency dependent manner. Our group has previously demonstrated that LTP-like TMS to the dorsolateral prefrontal cortex (DLPFC, a node in the Executive Control Network (ECN)) can decrease perceived pain and corresponding BOLD signal in the ‘Pain Network’ (7, 8, 10-12). The Pain Network is an expansion of the Salience Network (SN; insula, dorsal anterior cingulate) which includes the thalamus and somatosensory cortex(4-6). The analgesic effects of DLPFC TMS can be blocked by naloxone – suggesting that the analgesic effects of LTP-like DLPFC TMS are opiate mediated. Additionally, DLPFC TMS delivered postoperatively leads to less patient administered morphine use (PCA-pump) in the hospital and less opiate use in the outpatient setting (9). **These data all suggest that LTP-like DLPFC TMS is a promising candidate for treating pain (Strategy 1, Aim 1).**

An alternative strategy is to apply LTD-like stimulation to the medial prefrontal cortex (LTD-like mPFC rTMS (Strategy 2, Aim 2). This strategy is based on our understanding of functional neural architecture, wherein the SN is modulated by 2 other core networks: the executive control network (ECN) and the default mode network (DMN). As stated above, it is possible to attenuate activity in the SN through LTP-like TMS to the DLPFC, a node in the ECN. It is also possible to attenuate the SN through LTD-like TMS to the ventral medial prefrontal cortex (a node in the DMN). **The proposed study will be the first to employ a randomized, double-blind, sham-controlled design to parametrically evaluate the longitudinal effects of 16 days of rTMS to the DLPFC (Aim 1) or the MPFC (Aim 2) on self-reported pain and the brain's response to pain. This will be done in a cohort of patients recruited from the community as well as MUSC clinics with chronic lower back pain that have not been able to find adequate pain relief, whether or not they are using prescription opiates for 3 or more months.** Participants will be randomized to receive rTMS to the DLPFC (iTBS), MPFC (cTBS), or sham (50% at each site), using a Latin square randomization. Resting state connectivity will be collected 3 times: before the 1st day of TMS, after the 12th day of TMS, and before the 16th day of TMS (the last day administered).

Aim 1. Evaluate DLPFC rTMS as a tool to dampen pain and the engagement of the Pain Network. Hypothesis 1: DLPFC TMS will attenuate the baseline brain response to pain (Pain Network activity) and increase activity in the ECN when the patient is given instructions to ‘control’ the pain.

Aim 2. Evaluate MPFC rTMS as a tool to dampen pain and the engagement of the Pain Network. Hypothesis 1: MPFC TMS will also attenuate the baseline brain response to pain (Pain Network activity) but will not effect the ECN or SN when the patient is given instructions to ‘control’ the pain.

(Exploratory Aim): We will evaluate if there are rate-dependent effects between baseline SN connectivity with the ECN and DMN and the efficacy of each TMS strategy on subjective pain. Data will be analyzed by using multivariate pattern analysis (MVPA) (2014). While the primary outcomes will be MRI V1 vs V2, we will also examine the relative ‘durability’ of the effects on pain by comparing the MRI data at the end of all TMS visits between and within groups with factor analysis.

The relative efficacy of these strategies will directly translate to development of a large clinical trial investigating rTMS as an innovative, new treatment option for pain in patients with CLBP.

2.0 Background

BACKGROUND AND SIGNIFICANCE. Effective control of chronic pain is a top priority in the United States, as approximately 10% of adults have severe chronic pain – most of which is chronic lower back pain (CLBP)(National Institute of Health Statistics, 2006). CLBP is the leading cause of job-related disability and missed work. However, despite the advances in neuroscience over the past 20 years, we still largely treat CLBP pain with opiate narcotics, much as was done in the Civil War. In addition to their high abuse liability and dependence potential (1), only 30–40% of chronic pain patients declare they receive satisfactory (>50%) relief from their pain through pharmacological treatment (59). 96% of chronic pain patients using opiates reported insufficient control of pain, and on average opiate-using pain patients have experienced CLBP for more than a decade (59). A 2012 study demonstrated that patients with chronic pain resort to non-medical use of prescription opiates at high rates. This abundant use and misuse of opiates is a developing crisis, with 4.3 million users in 2014 (1), over 40% of prescription drug overdoses in the United States attributable to opioid analgesics (2), and total societal costs exceeding an estimated \$55 billion (3). Of individuals who misuse opioids, 80 to 90% initiated after having a legitimate prescription (13, 14) and 81% endorse pain as their reason for non-medical prescription opioid use (NMPOU) (14). **Consequently there is a critical need for new, treatments that can treat pain and reduce reliance on opiates in individuals with chronic pain. The goal of this R21 proposal is to evaluate 2 novel non-invasive brain stimulation strategies to mitigate pain in CLBP patients that are currently taking chronic opiates or that are seeking an alternative to relieve pain.**

Evaluating rTMS as a new, non-pharmacological approach to treating pain in opiate using individuals. TMS is a non-invasive brain stimulation method that is currently FDA-approved for the treatment of major depressive disorder. Repeated trains of stimulation can cause long-term potentiating (LTP) or depressing (LTD) effects on cortical areas directly under the coil (approximately 2cm depth) as well as monosynaptic projections (15-19). Our group has previously demonstrated that LTP-like TMS to the dorsolateral prefrontal cortex (DLPFC, a node in the Executive Control Network (ECN)) can decrease perceived pain as well as corresponding BOLD signal in the “Pain Network in healthy controls (7, 8, 30) and clinical populations (31-34). The Pain Network is an expansion of the Salience Network (SN; insula, dorsal anterior cingulate) which includes the thalamus and somatosensory cortex (4-6). The SN represents the attentional aspects of pain whereas the thalamus and somatosensory cortex represent somatic aspects of pain. The analgesic effects of DLPFC TMS can be blocked by naloxone, an opiate antagonist, suggesting TMS-induced analgesia is

[figure not shown]

Figure 1. Dynamic Interaction of Core functional connectivity networks. Adapted from Lerman et al 2014 JAMA Psychiatry. The Salience Network (SN), Executive Control Network (ECN), and Default Mode Network (DMN) represent 3 Core neural networks in the brain which are dynamically coupled. During pain, the SN & DMN are positively correlated (red), whereas the SN & ECN are anticorrelated (negatively correlated, blue). The outcomes of these aims will allow us to investigate baseline networks dynamic in CLBP patients treated with opiates (which has never been done) and test the hypotheses that increasing activity in the ECN (LTP-like TMS; Aim 1), and decreasing activity in the DMN (LTD-like TMS) will dampen pain in CLBP patients. The acute effect of 10 days of TMS as well as 1&2 month durability will be assessed.

opiate mediated (7, 8). [name] (Co-Investigator) was the first to demonstrate that when LTP-like DLPFC rTMS was delivered in the postoperative recovery room, patients used less morphine in the hospital and required less morphine long-term (9). **These data all suggest that LTP-like DLPFC TMS is a promising candidate for treating pain (Strategy 1, Aim 1).** This study will be the first to merge these findings, aiming to investigate the effects of TMS in both chronic opiate users, and individuals that cannot find any alternative to help relieve their pain.

An alternative strategy is to apply LTD-like stimulation to the medial prefrontal cortex (LTD-like mPFC rTMS (Strategy 2, Aim 2). This strategy is based on our understanding of functional neural architecture, wherein the SN is modulated by 2 other core networks: the executive control network (ECN) and the default mode network (DMN) (Figure 1). As stated above, it is possible to attenuate activity in the SN through LTP-like TMS to the DLPFC, a node in the ECN. It is also possible to attenuate the SN through LTD-like TMS to the medial prefrontal cortex (a node in the DMN) (Hanlon et al 2017). **The proposed study will be the first to employ a randomized, double-blind, sham-controlled design to parametrically evaluate the longitudinal effects of 12 days of rTMS, followed by 4 maintenance rTMS sessions, delivered to the DLPFC (Aim 1) or the MPFC (Aim 2) on self-reported pain and the brain's response to pain. This will be done in a cohort of patients recruited from the community as well as MUSC clinics with chronic lower back pain that have not been able to find adequate pain relief, whether or not they are using prescription opiates for 3 or more months.**

The scientific rationale for rTMS effects on pain in CLBP patients using chronic opioids.

TMS is the only non-invasive tool available to directly activate a specific neural circuit in humans. Opiate dependent individuals have reduced functional connectivity (35) between regions of the Pain Network (e.g. dorsal anterior cingulate cortex [dACC], insula, and thalamus (4-6, 36)) and the ECN (e.g. DLPFC (37)). Previous TMS studies have demonstrated that increasing activity in the ECN lowers perceived pain (27-29) and changes activity in nodes of the Salience Network (cingulate, insula) (30, 38, 39) which represent the attentional aspects of the pain network. One form of TMS is known as theta burst stimulation (TBS). This **biologically-relevant pulse sequence, is translationally derived from preclinical studies in learning and memory, and has powerful effects on cortical excitability in humans (40), wherein the same LTP-like effects of 10hz TMS are achieved much faster with TBS. As with traditional rTMS, TBS can induce LTP-like or LTD-like effects on** by applying the pulses intermittently (iTBS, LTP-like) or continuously (cTBS, LTD-like) (40). While the promise of inducing a lasting neuroplastic change in the Pain Network of opiate dependent individuals is enticing, it is not clear that the ‘plasticity potential’ of these circuits is as high in chronic opiate users as in healthy controls. Our preliminary data evaluating TMS to the DLPFC as a tool for dampening pain circuitry is promising (Aim 1, Strategy 1). However, given previously observed deficits in executive function in chronic pain patients on chronic opiates(44), it may be more efficacious to attenuate activity in the MPFC (Aim 2, Strategy 2) which would likely target the affective components of pain. The rationale for this alternative hypothesis is that in patients with chronic, ongoing pain, normal regulatory mechanism are disrupted, and pain processing is shifted towards more emotionally oriented circuits, such as the MPFC (34-36). This alteration in brain function encourages the exploration of alternative treatment locations in this population.

[figure not shown]

Figure LTP-like DLPFC TMS is known to attenuate the Pain Network (Taylor et al 2013, and others). The LTD-like vmPFC TMS attenuates the ACC and Insula(Hanlon et al, under review) and is reciprocally related to the DLPFC (Dunlop et al 2016, and others).

Early Feasibility Data: Quantitative Sensory Testing of pain in opiate using individuals after 10 sessions of rTMS (Strategy 1 and 2). Our group recently initiated a 10 day clinical trial of these 2 strategies as tools to decrease behavioral reports of pain. From June 2017 to October 2017 we were able to enroll and successfully acquire Quantitative Sensory Testing data from 10 individuals (5 of whom received each strategy for 10 days). 8 of the 10 remained enrolled for the full treatment. The 2 that didn't finish were terminated due to a Hurricane in our area (Sept 2017). This initial feasibility trial is promising and individuals appear to be receiving pain relief (as demonstrated by their continued engagement). However, without a rigorous sham control group or longitudinal neuroimaging data, the results of this pilot study will be limited to Quantitative Sensory Testing. Through this R21 mechanism we hope to be able to build upon the early success of this trial by including a rigorous, randomized, sham-controlled design which includes neuroimaging data necessary to understand mechanisms of action of these innovative new treatment approaches.

Aims 1 & 2 of this proposal will address the next critical steps in developing DLPFC or MPFC TMS as a new, innovative treatment option for pain: 1) Do multiple sessions of rTMS have a sustainable impact on pain in CLBP patients? And 2) Are there consistent patterns of neural activity to pain that serve as a predictive biomarker for TMS efficacy in these individuals?

INNOVATION. The proposed research is innovative in several ways. First, we are developing a conceptually innovative, alternative treatment strategy for chronic pain, which involves non-pharmacologic modulation of the circuits responsible for the perception of pain. This would be a significant conceptual advance for the field of chronic pain management. While LTP-like DLPFC rTMS has been promising as a tool for pain in non-opiate dependent individuals, the experiments outlined in this proposal represent a critical next step in their development for this CLBP population chronically using opiates. The knowledge gained from these Aims would be the basis for further examination in a larger Clinical Trial of TMS (R01) and would hasten the pipeline through which TMS could be developed as an evidence-based neuromodulation strategy for physicians and pain management providers to offer to patients with chronic lower back pain. Second, while most TMS investigations focus on the relative efficacy of stimulation at a single site (or a single functional network), by evaluating 2 strategies in this proposal we will be uniquely positioned to advance the field. Third, we are using a novel stimulation profile, theta burst stimulation (TBS) that was supported by our preliminary data, and is built on a foundation from learning and memory literature in preclinical research. This stimulation profile will significantly reduce the total time of active stimulation relative to 10 Hz rTMS, thus reducing patient burden.

3.0 Intervention to be studied (if applicable)

See section 2.0 for more information about the interventions being investigated.

4.0 Study Endpoints (if applicable)

Through this R21 mechanism we hope to be able to build upon the early success of this trial by including a rigorous, randomized, sham-controlled design which includes neuroimaging data necessary to understand mechanisms of action of these innovative new treatment approaches.

5.0 Inclusion and Exclusion Criteria/ Study Population

Participants. We will enroll 48 men and women 18-75 years old with CLBP. These individuals can also have a history of current prescription opioid use (>3 months) for the treatment of pain. Participants will be recruited through MUSC clinics as well as the outer community. Patients that have previously agreed to be contacted for research will be referred to the study or contacted via telephone. The risks of MRI and TMS to the unborn fetus are not well understood. Therefore, to be included, females must not be pregnant

as determined by a urine pregnancy test and must be utilizing reliable birth control during the course of the study.

Inclusion Criteria:

1. Age 18-75 (to maximize participation)
2. Can currently be using prescription opiates
3. Able to read and understand questionnaires and informed consent.
4. Is not at elevated risk of seizure (i.e., does not have a history of seizures, is not currently prescribed medications known to lower seizure threshold)
5. Does not have metal objects in the head/neck.
6. Does not have a history of traumatic brain injury, including a head injury that resulted in hospitalization, loss of consciousness for more than 10 minutes, or having ever been informed that they have an epidural, subdural, or subarachnoid hemorrhage.
7. Does not have a history of claustrophobia leading to significant clinical anxiety symptoms.

Exclusion Criteria:

1. Any psychoactive illicit substance use (except marijuana and nicotine) within the last 30 days by self-report and urine drug screen.
2. Meets DSM-V criteria for current axis I disorders of obsessive-compulsive disorder, bipolar affective disorder, schizophrenia, dissociate disorders, eating disorders, and any other psychotic disorder or organic mental disorder.
3. Has current suicidal ideation or homicidal ideation.
4. Has the need for maintenance or acute treatment with any psychoactive medication including anti-seizure medications and medications for ADHD.
5. Females of childbearing potential who are pregnant (by urine HCG), nursing, or who are not using a reliable form of birth control.
6. Has current charges pending for a violent crime (not including DUI related offenses).
7. Does not have a stable living situation.
8. Suffers from chronic migraines.

Inclusion of Women and Minorities

In 2016, the ratio of male:female individuals using opiates for pain was approximately 1:1. We will recruit in accordance with this ratio. There will be no exclusion criteria with respect to ethnic background.

The population of Charleston, SC is 52.2% White, 41.1% African American, and 1.6% Asian. 4.4% of the population is Hispanic/Latino. This is a relatively low percentage of Hispanic individuals based on national statistics. We will seek to enroll 5 Hispanic or Latino participants to be closer to the national average. Given the high concentration of African-Americans, all racial minorities will likely be black or African-American. We will strive however, to recruit a diverse population including American Indians, Asians, and Pacific Islanders if possible. As necessary, advertisements will be placed in newspapers and radio stations with primarily African-American or Hispanic readerships and listenership's (e.g., Charleston Post and Courier, The Charleston Free Press, WQMG FM).

6.0 Number of Subjects

48 participants will be enrolled in this research study.

7.0 Setting

General Facilities and Resources

The Medical University of South Carolina ranks in the upper third of federal research funds received by US medical schools and fosters cross-departmental collaborations as a means of integrating the basic and clinical sciences through its many research centers.

The Department of Psychiatry & Behavioral Sciences emphasizes excellence in clinical care, teaching, and research. MUSC Psychiatry is headquartered in its own building, the **Institute of Psychiatry** (IOP), where the majority of the department's faculty, residency training programs, research programs, and administrative offices are located. The department ranks among the top 15 psychiatry departments in the U.S., and the top 3 in the Southeast, in terms of funding from the National Institutes of Health. In FY2008 departmental faculty received 124 grant and contract awards, totaling \$24.2 million in extramural research support. Ongoing research projects range from basic neuroscience and brain imaging, to clinical pharmacology and treatment studies. The department's Center for Drug and Alcohol Programs, which includes a major NIH-funded Alcohol Research Center, involves extensive collaboration with basic science and other clinical departments. The addictions program was ranked 9th in the nation by U.S. News & World Report (2009). The main research divisions in the Department are the Brain Stimulation Laboratory, Center for Drug and Alcohol Programs, Clinical Neuroscience Division, Family Services Research Center, Geropsychiatry Division, National Crime Victims Center, Public Psychiatry Division, and Weight Management Center.

The Brain Stimulation Laboratory (BSL) is located in a series of labs and offices (>3000 square feet) primarily located on the 5th floor of the Institute of Psychiatry (IOP). BSL studies use electromagnetic approaches as either research tools investigating neuroscience questions or as investigational or FDA approved treatments for brain diseases. Techniques actively being used by BSL researchers and their collaborators include: transcranial magnetic stimulation (TMS), vagus nerve stimulation (VNS), transcranial direct current stimulation (tDCS), electroconvulsive therapy (ECT), deep brain stimulation (DBS) and epidural cortical stimulation (epCS). MUSC's BSL team has been a world leader in TMS research since 1995, performing basic research studies using TMS as well as using TMS in clinical trials for depression, pain and addiction.

Facilities and Resources Specific to the PI:

[name] primary office and laboratory is in the Brain Stimulation Division of the Department of Psychiatry. She will utilize the resources of the Brain Stimulation Laboratory.

[name] manages the BSL suite located in the Center for Biomedical Imaging along with [name]. This suite contains a room (10ft x 10 ft.) dedicated for TMS stimulation. This room currently contains 2 computers, a desk for patient interviewing, and a Magstim Bistim TMS system.

8.0 Recruitment Methods

Participants with chronic pain will be recruited via flyers placed throughout the MUSC campus, community, MUSC clinics, broadcast messages, Craigslist, and via phone calls to individuals that have participated in previous studies with our group and have given permission to be contacted if other studies become available. Participants will also be recruited at community events using advertising materials. At these events, participants will have the opportunity to fill out a card stating that they are interested in being contacted about our research studies. These cards will contain their name, email, and phone number. They will be placed in a secure, opaque container in order to protect their identity, and will be destroyed after an initial contact has been made.

A chart review will be conducted for research purposes. Potentially eligible patients will be identified. The potentially eligible patients in the PIs practice will be informed about the study as the PI feels is appropriate. Then potential patients who have agreed to be contacted for future research by logging their MUSC Research Permissions preferences in MyChart will be contacted by phone and invited to participate. All other patients will be contacted through their providers to be informed of the study if the provider feels it is appropriate.

Subjects that are currently enrolled in the study will also be invited to participate in the recruitment of other subjects. If they choose to participate, they will be given coupons that can be distributed to other people (e.g., peers, acquaintances) who they think could be eligible and interested in the study. The individuals that are given these coupons can contact the study office themselves if interested in participating. If they decide to participate in the study, the currently enrolled subject will be given \$10 for each coupon received from the enrollment of new participants. This recruitment tool is completely voluntary and if subjects elect not to participate, participation in this study will not be affected in any way. Participants will be screened and provide written informed consent to participate which will be obtained by study personnel. Participants will have an opportunity to ask questions and can discontinue participation at any time without penalty.

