Strategy 2: cTBS to the vmPFC. For continuous theta burst stimulation (Aim 2), participants will receive 1 train of stimulation over the left frontal pole (FP1) (each train: 3 pulse bursts presented at 5Hz, 15 pulses/sec for 40 sec, 600 pulses/train, 110% RMT, MagPro; 600 pulses total) using a figure 8 coil (Coil Cool-B65 A/P). This protocol has been shown to attenuate the mPFC and striatum in cocaine dependent individuals in the past (61-63) and has been more effective than 1200 or 1800 pulses of cTBS in attenuating depression (The time between the end of the TBS procedures and the beginning of the behavioral assessments, as well as the scalp-to-cortex distance (which effects the actual TMS dose given to the cortex) will be compiled and used as covariates in subsequent analyses.

ACTIVE SHAM system. The MagVenture MagPro system has an integrated, active sham which passes current through two surface electrodes placed on the scalp. The electrodes will be placed on the left frontalis muscle for all sessions. A patient ID card will randomize participants to receive either real or sham stimulation. This system maintains blinding by a gyroscope in the coil which indicates to the clinical staff whether the coil should be rotated up or down for this participant once the card is entered into the machine. One side of the coil is active, the other is sham. The integrity of the double-blind procedure will be assessed by asking the patients and study personnel rate their confidence regarding whether they thought they received real or sham (scale 1-10).

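### Past participants of the group's own studies may be recruited and prior TMS is neither excluded nor recorded, which leaves a modest threat to blinding and to generalisability

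*Combined protocol and SAP*

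**What the plan says.** **Recruitment.** Among other sources, Section 8.0 recruits "via phone calls to individuals that have participated in previous studies with our group and have given permission to be contacted". It names no study and leaves none out. Section 9.0 then describes phone screening of people who agreed earlier to be contacted.

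**The group's earlier TMS work.** Section 2.0 (Early Feasibility Data) states: "Our group recently initiated a 10 day clinical trial of these 2 strategies as tools to decrease behavioral reports of pain". The pilot is headed "Quantitative Sensory Testing of pain in opiate using individuals after 10 sessions of rTMS (Strategy 1 and 2". It managed to "acquire Quantitative Sensory Testing data from 10 individuals (5 of whom received each strategy for 10 days", and "8 of the 10 remained enrolled for the full treatment". Its limitation is given as "However, without a rigorous sham control group or longitudinal neuroimaging data". Section 7.0 adds that the laboratory runs TMS trials in depression, pain and addiction.

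**Eligibility.** Section 5.0 has seven inclusion and eight exclusion items. None concerns earlier TMS, earlier participation or a washout. The exclusion text under Participants in Section 10.0 refers to the usual MRI and TMS exclusions and gives safety examples; prior TMS is not among them.

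**Analysis.** The covariates in Section 10.0 include sessions received by dropouts, scalp-to-cortex distance, sex, depression score, duration of opiate use and opiate dose timing, but not prior TMS. No stratification by prior TMS is described. The quality assurance plan in Section 13.0 has a general check of baseline comparability.

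**Blinding.** Section 10.0 specifies an active sham with scalp electrodes, and says: "The integrity of the double-blind procedure will be assessed by asking the patients and study personnel rate their confidence". No rule is given for using those ratings.

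**The concern.** What this trial adds to the pilot is a randomised, double-blind, sham-controlled comparison. That comparison is weaker if some participants already know what real stimulation feels like. Everyone in the pilot is reported as having received one of the two strategies, so whatever the pilot's masking, its participants are experienced with real stimulation.

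The outcomes leave room for this to matter. The thermal thresholds are signalled by the participant, and pain, discomfort and urge to use a pain reliever are self-rated. A participant who recognises sham may report less relief, that is, higher pain or a lower threshold. This makes sham look worse and the active arms look better. Because it happens after allocation, randomisation does not remove it.

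Two other routes matter in a different way. If earlier stimulation has a lasting effect, the baseline scan and baseline pain are not untreated values, although Section 10.0 uses scan 1 against scan 2 as the primary comparison and baseline connectivity as a predictor. And Section 2.0 reads staying in the pilot as a sign of benefit ("individuals appear to be receiving pain relief (as demonstrated by their continued engagement"). By the same reasoning, people who felt relief may be readier to come back. Effect sizes meant for a later R01 would then apply less well to TMS-naive patients with chronic lower back pain.

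**Working it through.** **1. Can an experienced person enter?** Set the texts side by side. Section 8.0 opens a route for past participants, Section 2.0 shows that some past participants received these strategies, and Sections 5.0 and 10.0 contain no item that stops them on that ground. The plan permits it. Whether anyone does enter is not stated.

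**2. Inputs.** Allocation is 16 real DLPFC, 16 real MPFC and 16 sham, 48 in all (Section 10.0). The pilot had 10 people, 8 of them completers (Section 2.0). The plan gives no number of returners and no other figure on this point, so there is no planned value to reproduce. I assume k returners, with k = 10 as the most the reported pilot can supply. I also assume that a returner who recognises the assignment shifts the reported outcome by e = 0.5 SD.

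**3. Numbers per arm.** Share of the sample = k/48; expected per arm = 16 × k/48 = k/3.

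**4. Bias from recognition.**
- Shift in one arm only (for example sham): e × k/48.
- Shift in opposite directions in real and sham: 2 × e × k/48.

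**5. Chance imbalance.** With k returners allocated at random to 16/16/16, the expected difference between an active arm and sham is 0. The last column gives the probability that the two differ by 3 or more returners.

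| k (assumed) | Share of 48 | Expected per arm | Bias, one arm (SD) | Bias, opposite (SD) | P(difference of 3 or more) |
|---|---|---|---|---|---|
| 1 | 2.1% | 0.33 | 0.01 | 0.02 | 0 |
| 2 | 4.2% | 0.67 | 0.02 | 0.04 | 0 |
| 4 | 8.3% | 1.33 | 0.04 | 0.08 | 11% |
| 8 | 16.7% | 2.67 | 0.08 | 0.17 | 24% |
| 10 | 20.8% | 3.33 | 0.10 | 0.21 | 28% |

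Example: for k = 4, one arm, 0.5 × 4/48 = 0.04; for k = 10, opposite, 2 × 0.5 × 10/48 = 0.21. Bias is proportional to e, so at e = 1.0 SD every bias value doubles, to at most 2 × 1.0 × 10/48 = 0.42 SD.

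**6. If recognition needs the same site.** Each pilot participant is reported under one strategy, and sham is split half and half by site. The chance of sham at the site already experienced is 1/3 × 1/2 = 1/6. With 8 to 10 returners that is 8/6 = 1.3 to 10/6 = 1.7 people, and the one-arm bias halves: for k = 4 to 10, 0.5 × 0.5 × k/48 = 0.02 to 0.05 SD.

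**The case against.** The strongest reply is that the plan only permits this, and that much of the harm has to be inferred.

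- **A reader might infer that pilot participants will be phoned.** Section 8.0 names no study. The pilot heading describes opiate-using people and does not say they had chronic lower back pain, which this trial requires. The Section 10.0 exclusion list is open-ended. This stands: entry is possible, not shown.
- **A reader might infer that the pilot was unblinded.** The document says only that it lacked a rigorous sham control group. Its masking is not described.
- **A reader might infer that exposure would be recent and still active.** The pilot data are dated June to October 2017, while Section 13.0 cites a policy posted on February 20, 2019, about 16 months after the end of that period. Enrolment may have begun under an earlier version, but no short interval is documented. Section 2.0 poses lasting benefit as an open question, which is not evidence of carry-over.
- **A reader might infer that carry-over and selective return bias the sham contrast.** Both precede randomisation and are equal across arms in expectation. They change baseline levels and who the result applies to, and can be unevenly spread by chance.
- **Blinding is already protected in part.** The active sham imitates sensation and the confidence ratings may reveal a problem. They lessen or detect unblinding. They do not remove it, and the plan does not say what follows if the ratings differ by arm.

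What remains after all this is the gap itself: prior TMS is neither excluded, nor given a washout, nor named in the analysis.

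**Conclusion.** The point holds in a limited form. As written, the plan can randomise people who have had real TMS, including these same strategies, and the analysis would not distinguish them. Only recognition of real or sham stimulation can bias the active-versus-sham contrast systematically. If sham participants report less relief on recognising it, the contrast is inflated; lower pain reports in the sham arm would shrink it.

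The size is about 0.04 to 0.21 SD for 4 to 10 returners, and 0.01 to 0.04 SD for 1 or 2. This rests on three assumptions that the documents do not settle: the number of returners, a 0.5 SD shift, and recognition by every returner in the affected arm or arms. A share of 17% to 21% of the sample needs 8 to 10 of the 10 pilot participants to return. That is an upper range for the pilot, not an expectation. The laboratory's other TMS studies could add people, but the documents give no basis for a number.

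This is a cheap improvement of low to moderate severity. It does not show that the sham comparison is invalid.

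**What to change.** Add to the exclusions in Section 5.0, and match in Section 10.0: *Any previous rTMS or TBS treatment, including participation in the group's earlier TMS pain study.* Ask about it at the phone screen described in Section 9.0.

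If anyone with prior TMS is already enrolled, record it for each participant and report the active-versus-sham estimates with and without them.

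A full exclusion is not the only defensible route. A stated washout, or recording prior TMS with stratification or adjustment and a TMS-naive sensitivity analysis, would address the same gap, though with 16 per arm the exclusion is simpler.

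The cost is one eligibility line and one screening question. The downside is the loss of a few easily reached candidates.
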